### **1.3. Population to be studied**

It is planned that this study will enroll no fewer than 328 patients with a range of COPD severities, Eligible patients will have spirometry-defined COPD (i.e. post-bronchodilator FEV1/FVC<0.7), be over 40 years' of age, be current smokers or ex-smokers with at least 10 pack-years of smoking exposure and be in a stable clinical state (as judged by the investigator) at point of recruitment.

## 2. STUDY OBJECTIVES AND RATIONALE

### 2.1. Hypothesis

Control in COPD is a new conceptual dimension requiring demonstration of both low impact and clinical stability. The developers of the concept hypothesize that a status of control in COPD will be associated with better clinical outcomes (reduced frequency of exacerbations and mortality and improved health-related quality of life); reduced rate of decline in lung function and/or BODE/BODEx and reduced direct COPD-related healthcare costs.

### 2.2. Primary objectives

Following the publication of the Concept of COPD Control (6) and building on a retrospective pilot study designed to characterize evaluate the clinical implications of COPD control status within a UK primary care COPD population, the aim of this study is to validate the concept of control utilizing an international, multi-centre prospectively trial design.

The primary aims of the study will be to evaluate, in an international cohort of routine care / unselected COPD patients, the:

- 1) Levels of COPD control (vs poor COPD control), and
- 2) Clinical implications of control status.

### 2.3. Secondary objectives

With a view to identifying opportunities to refine the tool to optimize its clinical utility and ability to guide treatment decisions to improve COPD outcomes (reduce disease burden and improve stability) and to identify patients in whom it may be best targeted (in terms of beneficially modifying outcomes and achieving cost efficiencies, a number of secondary objectives will also be evaluated. The secondary objectives of the study will aim to:

- 1) Compare the utility of the COPD Control (as defined) as a tool to identify COPD impact and stability with the CAT and CCQ;
- 2) Evaluate the role of “adequate” (i.e. guideline-recommended) treatment prescribing on COPD control.
- 3) Identify demographic and clinical characteristics associated with COPD control status

[figure not shown]

Table 4. Visit summary

Visit number	-1	0	1, 2 and 3
Time of Visit	Inclusion	Baseline 3 months	9, 15 and 21 months or discontinuation
Inclusion/Exclusion criteria	✓		
Information & Informed consent	✓		
Clinical assessment	✓	✓	✓
Assessment of exacerbations since last visit*	✓	✓	✓
Assessment of clinical status since last visit	✓	✓	✓
CAT/CCQ	✓		
Adverse events		✓	✓

## 4.2. Eligibility Criteria

### 4.2.1. Inclusion criteria

Eligible patients must meet the following inclusion criteria, be/have:

- 1) Spirometry-defined COPD (i.e. post-bronchodilator FEV1/FVC<0.7)
- 2) Age ≥40 years
- 3) Smokers or ex-smokers of at least 10 pack-years
- 4) In stable state (as judged by the investigator) at point of recruitment

### 4.2.2. Exclusion criteria

Patients will be excluded from the trial if any of the following are true, they:

- 1) Have any chronic concomitant respiratory condition other than asthma or bronchiectasis (e.g. cystic fibrosis, lung fibrosis)
- 2) Have severe comorbidity with a life expectancy shorter than 2 years

- 3) Are unable to understand the instructions of the study or to fill the questionnaires
- 4) Are unwilling to sign the informed consent
- 5) Are participating in another clinical study or clinical trial.

### **4.3. Outcomes**

#### **4.3.1. Primary outcomes**

The primary study outcome will be measured over the 21-month follow-up period.

The primary outcome of interest will be the difference in (annualized) rates of a composite endpoint (“Mortality, hospitalisations and serious COPD morbidity”) for patients controlled vs uncontrolled at baseline. The composite endpoint is defined as occurrence of any of the following:

- For COPD: unscheduled visits to the physician; emergency room attendance
- An exacerbation of COPD
- All-cause: hospitalization or mortality

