**General Design and Methodology:**

This is a 21-month pragmatic non-interventional trial comprising one baseline assessment and 4 follow-up visits.

**Objectives:** The primary aims of the study will be to evaluate the:

- Levels of COPD control (vs poor COPD control) in an international cohort of routine care COPD patients, and
- The clinical implications of control status.

Secondary objectives of the study are to:

- Compare the utility of the COPD Control (as defined) as a tool to identify COPD impact and stability with the CAT and CCQ;
- Evaluate the role of “adequate” (i.e. guideline-recommended) treatment prescribing on COPD control.
- Identify demographic and clinical characteristics associated with COPD control
- Evaluate the cost-utility of patients with controlled (as compared to poorly controlled) COPD.

**Number of Patients Planned:** 328

**Study Population:** It is planned to enrol approximately 328 patients older than 40 years with a diagnosis of COPD. The diagnosis of COPD will be based on a post-bronchodilator FEV1/FVC<0.7 in patients smokers or smokers of at least 10 pack-years, in accordance with the Global Initiative for Obstructive Lung Disease (GOLD).

**Length of the Study:** Length of the study will be approximately 21 months from baseline screening to final patient follow-up.

**End of the Study:** Last patient’s last visit.

**Inclusion Criteria:** Patients may be included in the study if they meet all of the following criteria:

- Spirometry-defined COPD (i.e. post-bronchodilator FEV1/FVC<0.7)
- Age ≥40 years
- Smokers or ex-smokers of at least 10 pack-years
- In stable state (as judged by the investigator) at point of recruitment

**Exclusion Criteria:** Patients will be excluded from participating in this study if they meet any of the following criteria:

- Have any concomitant chronic respiratory condition other than asthma or bronchiectasis (e.g. cystic fibrosis, lung fibrosis)
- Have severe comorbidity with a life expectancy shorter than 2 years
- Are unable to understand the instructions of the study or to fill the questionnaires
- Are unwilling to sign the informed consent
- Are participating in another clinical study or clinical trial

**Investigational Product:** NA (non-interventional study)

**Placebo:** NA (non-interventional study)

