### Stability

Clinical stability over time is defined as a composite of the following over a 3-month evaluation period:

1. Absence of exacerbation (including the inherent phase of recovery from the exacerbation), AND
2. Absence of significant clinical worsening\* during a period of time, that is, that stability includes the absence of significant clinical changes and/or the presence of improvement (positive changes).

\*The CAT and CCQ have demonstrated potential utility in evaluate clinical changes over time (4,5). Clinically significant deterioration has been described as being associated with a change of ≥2 CAT points (6) and/or a change of ≥0.4 CCQ points (6).

Table 2. Definition of COPD stability by COPD Severity Category

Clinical stability over time (3-month evaluation period)		Mild to moderate severity (BODE/Ex ≤ 4 points)		Severe/very severe COPD (BODE/Ex > 5 points)	
		Stable	Unstable	Stable	Unstable
No Exacerbations	Exacerbations	None	≥1	None	≥1
AND					
No Clinical Worsening	Changes in the CAT	<2	≥2	<2	≥2
	AND/OR				
	Changes in the CCQ	< 0.4	≥ 0.4	≤ 20	>20

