#### 4.4.2. Visits 0–3: Baseline and follow-up assessment

In baseline visit (3 months after screening visit) patients will be included in one of the study groups (controlled patients or uncontrolled patients) according definitions. The following data will be collected at the time of each follow-up visit in order to assess disease stability between follow-up visits and disease control at time of each visit.

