**Table 7. Follow up visit date capture**

Visit numbers: 0-3 (inclusive)
Time of Visit: Follow-up (3 months; 9 months; 15 months; 21 months)
Information & Informed consent
Clinical assessment (additional to inclusion/exclusion criteria): 
 
• History of previous exacerbations/hospitalisations
 
• Respiratory symptoms
 
• Respiratory medications
 
• Mood (PhQ-4)
 

Assessment of COPD Impact 
 
• Sputum 
 
– Absent
 
– Present: colour = white
 
– Present: colour = dark
 
 
 
• Daily physical activity (time walked/day) 
 
– <30 minutes
 
– ≥30 minutes but <60 minutes
 
– ≥60 minutes
 
 
 
• Dyspnea (mMRC score) 
 
– 0–1
 
– 0–2
 
– ≥2
 
– ≥3
 
 
 
• Rescue medication use (SAB) 
 
– Number of times in the last week (0-3; >3)
 
– Number of times a day (0-2; >2)
 
– ≥3
 
 
 

COPD Severity: BODE/BODEx Index (calculated; components captured as part of other assessments outlined)
CAT
CCQ

 Visit 0 and 3 only

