## 9. STATISTICAL ANALYSIS

### 9.1. General

Intention-to-treat and per-protocol analyses will be undertaken. For the Intention-to-treat analysis, all patients entered into the study will be included in the analysis. For the per-protocol analysis, all patients entered who complete the study as per protocol (defined as attending baseline and all follow-up visits irrespective) will be included.

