### 13. TIME SCHEDULE AND DELIVERY

The total length of the study will be approximately 24 months from screening the first patient to completion of the last patient visit. The patient will be in the study for 24 months, attending 5 visits at 6-monthly visits.

The approximate timelines for the different phases of the study – data collection through to publicaito are detailed in Table 9, below.

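### The primary outcome's 21-month window, read literally, includes the three months used to define control, which biases the comparison in favour of controlled patients

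*Protocol*

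**What the plan says.** **Outcome window.** Section 4.3.1 defines the primary outcome as the difference in annualised composite rates between patients controlled and uncontrolled at baseline. COPD exacerbation is one component. On timing it says: "The primary study outcome will be measured over the 21-month follow-up period".

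**Start of the 21 months.** The protocol summary says: "Length of the study will be approximately 21 months from baseline screening to final patient follow-up".

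**Visits.** Table 4 places Visit -1 at inclusion, Visit 0 (baseline) at 3 months, and Visits 1 to 3 at "9, 15 and 21 months or discontinuation". Table 7 lists "Follow-up (3 months; 9 months; 15 months; 21 months". No visit is scheduled after month 21.

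**Group assignment.** Section 4.4.2 says: "In baseline visit (3 months after screening visit) patients will be included in one of the study groups".

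**Definition of control.** Control requires low impact and stability over a three-month evaluation period. The first stability criterion is "Absence of exacerbation (including the inherent phase of recovery from the exacerbation), AND". It applies in both severity categories. At Visit 0 the evaluation period is months 0–3.

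**Other durations and the analysis set.** Section 13 says "The patient will be in the study for 24 months, attending 5 visits at 6-monthly visits", and section 4.3.2 also mentions a 24-month follow-up. For the intention-to-treat analysis, section 9.1 says "all patients entered into the study will be included in the analysis".

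**The concern.** An exacerbation in months 0–3 makes a patient uncontrolled at Visit 0. If the outcome is counted over the same months, that exacerbation is also scored as an outcome of the uncontrolled group. Controlled patients contribute three months of person-time in which they cannot have had an exacerbation. Part of the difference then comes from the definition, not from what follows.

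The study's purpose (section 2.2) is to validate control as a concept, and its hypothesis is that control goes with better outcomes. A window that favours control before any follow-up has occurred weakens the primary test of that hypothesis. The same issue reaches the time-to-first-event outcomes in 4.3.2, which have no stated origin, and the year-1 logistic and multinomial models in 9.3.3. Patients entered but lost or dead before Visit 0 have no control status, so they cannot be placed in either group.

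**Working it through.** **1. The plan's own figures.** Inclusion at month 0 and last visit at month 21 reproduce the 21 months. Classification is at month 3, and 21 − 3 = 18. The only way to reach 21 months within the schedule is to start at Visit -1.

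The 285 patients in section 4.5 (1.2 versus 0.72 per year, two-sided 5%, 90% power) can be approximated. The probability of at least one event in a year is 1 − exp(−1.2) = 0.699 versus 1 − exp(−0.72) = 0.513, and comparing these proportions 1:1 needs 288 in total. The macro's formula is not given, so this is a near match only.

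**2. Inputs for the bias.** From section 4.5: 1.2 exacerbations per year, 55% controlled, 285 evaluable patients. From section 9.3.3: Mann-Whitney test. Assumptions: Poisson counts, three months = 0.25 year, the same true rate in everyone, low impact independent of that rate.

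**3. No true difference, exacerbations only, 21-month window.**
- Expected events per patient, months 3–21: 1.2 × 1.5 = 1.8 in both groups.
- Months 0–3, whole cohort: 1.2 × 0.25 = 0.30 per patient, all in the uncontrolled 45%: 0.30/0.45 = 0.67 each. Controlled: 0.
- Controlled: 1.8/1.75 = 1.03 per year. Uncontrolled: (1.8 + 0.67)/1.75 = 1.41 per year.
- Ratio 1.8/2.467 = 0.73, a 27% apparent reduction against the 40% hypothesised.

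With a constant rate the ratio is 1.5/(1.5 + 0.25/(1 − share controlled)), whatever that rate is: 0.78 at 40% controlled and 0.64 at 70%.

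**4. Sensitivity, still with no true difference.** The first two variations use assumed rates, because the documents give none.
- Other composite events at 0.6 per year in both groups add 0.6 × 1.75 = 1.05 each: 2.85/3.517 = 0.81. At 1.2 per year they add 2.1: 3.9/4.567 = 0.85.
- Exacerbation rate of 0.6 per year in months 0–3: 0.15/0.45 = 0.33, so 1.8/2.133 = 0.84. At 0.3 per year: 0.075/0.45 = 0.17, so 1.8/1.967 = 0.92.

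Simulated false-positive rates of the Mann-Whitney test with 285 patients (repeat runs differ by about one to three percentage points):

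| Scenario | Ratio | False positives |
|---|---|---|
| Exacerbations only, 1.2/year, 55% controlled | 0.73 | about 97% |
| Same, 40% controlled | 0.78 | about 83% |
| Plus other events, 0.6/year | 0.81 | about 87–89% |
| Plus other events, 1.2/year | 0.85 | about 77–78% |
| Early rate 0.6/year | 0.84 | about 48–49% |
| Early rate 0.3/year | 0.92 | about 17% |
| First scenario, counted from month 3 | 1.00 | about 5% |

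**5. If control does predict events.** Take 1.2 versus 0.72 per year after Visit 0, a true ratio of 0.60. Controlled over 21 months: 0.72 × 1.5/1.75 = 0.617.
- If the uncontrolled have 1.2 × 0.25 = 0.30 early events each, their rate is (1.8 + 0.30)/1.75 = 1.20 and the ratio is 0.51.
- If they carry all early events of a cohort averaging 1.2 × 0.45 + 0.72 × 0.55 = 0.936 per year, each has 0.25 × 0.936/0.45 = 0.52. Their rate is 1.326 and the ratio is 0.47.

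**6. Power without months 0–3.** An exponential two-rate formula at the planned rates and power needs about 224–228 patients with 18 months of follow-up and 210–214 with 21. Both are below 285.

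**The case against.** **The start of counting is not stated.** Section 4.3.1 names no day, and it compares patients by control status at baseline, which section 4.4.2 puts at month 3. The 21 months may be loose wording for study length. Alternatively, 21 months after a month-3 baseline would end at month 24, which fits the 24-month statements in 4.3.2 and 13 and the interval in Table 9 from end of recruitment (July 2016) to complete data collection (July 2018). This stands in part. A reader might infer that the plan definitely counts months 0–3, and the documents do not support that certainty. But the summary runs the 21 months from screening, both visit tables end at month 21, and a start at Visit 0 gives 18 months under that schedule. The literal reading is the overlapping one.

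**The largest figure is not for the composite.** The 97% models exacerbations alone. Unscheduled COPD visits that do not meet the exacerbation definition and hospitalisations for other causes are not excluded by classification, and they dilute the artefact. COPD emergency attendance and hospitalisation do count as exacerbations (sections 4.4.1.3 and 8.1), so they overlap as well. Patients must also be stable at recruitment, so early rates may be below 1.2 per year. These points stand, so the size is given as a range.

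**A real effect may exist.** If patients differ in their underlying rate, past exacerbations do predict later ones. With an assumed negative binomial dispersion (k = 1), the 18-month ratio is about 0.61 and the 21-month ratio about 0.47. It would therefore go too far to infer that any positive result is an artefact.

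**Conclusion.** The point holds as a defect in the wording of the primary outcome. Followed literally, section 4.3.1 counts the classification window as outcome time, and no statement elsewhere removes it. The bias favours control in every scenario examined. With no true association, the spurious ratio runs from about 0.73 (about 97% false positives) to about 0.92 (about 17%) at 55% controlled. Where it falls depends on the rate of other composite events and the early exacerbation rate, neither of which the documents give. With a true association, the window inflates it, for example from 0.60 to about 0.47–0.51. All figures assume Poisson counts except the negative binomial case.

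Two stronger readings are not supported: that about 97% is the trial's false-positive rate, since it rests on exacerbations alone at a constant rate, and that a positive result would carry no information, since a genuine association may lie beneath the inflation.

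**What to change.** - **Section 4.3.1:** set time zero at Visit 0. Count events and person-time only from Visit 0 to month 21, which is 18 months under the stated schedule.
- **Section 4.3.2:** use the same origin for the exacerbation rate and both time-to-first-event outcomes.
- **Section 9.3.3:** start year 1 of the logistic and multinomial models at Visit 0.
- **Section 9.1:** base the controlled-versus-uncontrolled comparison on patients classified at Visit 0, and describe separately those lost or dead before it.
- **Durations:** reconcile the 21-month statements (summary, 4.3.1) and 24-month statements (4.3.2, 13) with the visit schedule. If the sponsor intends 21 months after classification, the schedule as written does not provide it.

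Under the stated schedule this is wording only, with no new visits or data. The cost is that outcome follow-up is stated as 18 months instead of 21. By the formula in step 6 of the working, that does not push the requirement above 285.

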#### **4.3.2. Secondary outcomes**

The secondary outcome for the study will be:

- 1) The (annualized) rate of exacerbations in patients controlled and uncontrolled at baseline
- 2) Time to the first composite event in patients controlled and uncontrolled at baseline
- 3) Time to the first exacerbations in patients controlled and uncontrolled at baseline
- 4) Comparison of CAT and CCQ as tools to identify impact and stability in COPD (i.e. a comparison of their scores' alignment with other relevant scores over the 24-month follow up period).
- 5) Distribution of control level across in those receiving guideline vs non-guideline recommended therapy (i.e. stratification of control across different treatment groups)
- 6) Demographic and clinical characteristics associated with poor control of COPD (i.e. comparison of control status across different demographic groups).

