## 1. BACKGROUND

### 1.1. Introduction

Chronic obstructive pulmonary disease (COPD) is a broadly heterogeneous condition. Optimum therapeutic outcomes require treatment to be tailored to the different clinical characteristics and severity of each patient (7-9). To a certain extent, the Spanish Guidelines for COPD (GesEPOC) represent a model of transition towards personalized medicine (10). In these guidelines pharmacological treatment is established with a combination of two essential elements: (i) the determination of the clinical phenotype and (ii) evaluation of the level of severity with the use of a multidimensional index. Multiple therapeutic alternatives emerge from the interaction between these two axes (clinical phenotype and the level of severity), constituting the first step towards individualization of treatment, which has been followed by other national clinical guidelines (11).

However, this approach can overlook changes in the day-to-day activities or symptoms of the patient, changes that may warrant modifications to their existing treatment. Within each clinical phenotype and each level of severity of COPD there are patients with a range of different “expressions” (i.e. symptoms, activity limitations, short-term changes) of their disease. Thus, the concept of disease control may help to better assess the state of the patients and their likely response to treatment. A third axis (control of the disease) should help in therapeutic decision making and has been recently proposed (12,13).

The concept of control has been extensively developed in asthma but little-explored in COPD. Recently, however, Soler-Cataluña et al proposed a new definition/concept of control for COPD. The concept aims to help describe the current clinical “situation” of the patient and to provide a tool that will help guide optimum treatment approaches for patients with COPD(14).

The definition has two components: (i) COPD impact and (ii) COPD stability. “Impact” is a cross-sectional concept that evaluates the clinical status of a patient. It is static assessment corresponding to a specific moment and can be assessed by questionnaires (i.e. the COPD Assessment Test [CAT] or the Clinical COPD Questionnaire [CCQ]) or evaluated based on a patient’s degree of dyspnea, use of rescue medication, level of physical activity and sputum colour. The temporal evolution of this impact (i.e. COPD stability) is a dynamic term. “Stability” is a

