### ***COPD and other medications***

A review of COPD and concomitant therapies currently prescribed and used by the patient will be performed to support evaluation of the secondary objective (role of guideline-recommended therapy on COPD control).

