## **5. PATIENT MANAGEMENT DURING THE CONDUCT OF THE STUDY**

In accordance with a pragmatic study design, patients will receive usual care by their own physician during the conduct of the study. The time between visits, 3-6 months, is in accordance with usual clinical practice and the recommendations of guidelines for regular follow-up of moderate to severe COPD patients.

Other than attending the required number of clinical visits (baseline, and 4 follow-up visits) patients will not be contacted by the research team in relation to this study.

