### 9.3. Statistical analysis

Baseline and outcome variables will be analysed as a complete dataset and by treatment groups (split by baseline COPD severity).

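### The outcome set for the guideline-treatment objective is an unadjusted distribution of control, which cannot by itself show the role of treatment on control

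*Protocol*

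**What the plan says.** Protocol section 2.3 lists as its second objective the role of adequate, meaning guideline-recommended, "treatment prescribing on COPD control". Section 4.3.2, item 5, gives the matching outcome: "Distribution of control level across in those receiving guideline vs non-guideline recommended therapy (i.e. stratification of control across different treatment groups". That item states no adjustment and no treatment time point.

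Other sections bear on it:

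- Section 5: "patients will receive usual care by their own physician during the conduct of the study". Treatment is not allocated.
- Section 1.1 says the Spanish guideline sets drug treatment from two elements: "the determination of the clinical phenotype and (ii) evaluation of the level of severity with the use of a multidimensional index". It adds: "Multiple therapeutic alternatives emerge from the interaction between these two axes (clinical phenotype and the level of severity".
- Section 4.4.1.3, under COPD and other medications (Visit -1): "A review of COPD and concomitant therapies currently prescribed and used by the patient will be performed". The sentence goes on to tie this review to the guideline-therapy objective.
- Section 4.4.2 assigns patients to the controlled or uncontrolled group at Visit 0, three months later. Table 7 shows respiratory medication recorded again at Visits 0 to 3.
- Section 9.3 analyses baseline and outcome variables as a whole and "by treatment groups (split by baseline COPD severity".
- Section 9.3.4 plans a stepwise multivariable logistic model with control as the dependent variable. All variables from the univariate analyses are candidates, and the threshold for entry or deletion is 0.01. Section 9.3.1 lists COPD medications among the baseline variables.

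**The concern.** The objective is directional: prescribing is the exposure and control is the response. The outcome is a table. In a usual-care cohort, patients on guideline-concordant therapy may differ from the rest in severity, phenotype, exacerbation history and health system, and these can also bear on control. BODEx contains dyspnoea and exacerbations (section 4.4.1.3), and the control definition also uses mMRC and exacerbations. A difference between the two columns could therefore come from who gets concordant treatment. A real difference could equally be masked.

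Section 2.3 says the secondary objectives are meant to help refine the tool so that it can guide treatment decisions. An unadjusted contrast is weak ground for that.

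**Working it through.** **Is an adjusted analysis specified for this comparison?**

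| Section | What it provides | What it leaves open |
|---|---|---|
| 4.3.2, item 5 | Control by guideline versus non-guideline therapy | Adjustment, time point |
| 9.3 | Two-level severity split by treatment groups | Phenotype, prior exacerbations, country. Treatment groups are not defined; the groups named in 9.3.4 are controlled and uncontrolled |
| 9.3.4, ANCOVA | Confounders as covariates for EQ5, CCQ, lung function, BODE | Does not cover item 5 |
| 9.3.4, stepwise model | Multivariable model for control | Concordance is not a named exposure; it or any confounder can drop out at 0.01 |

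The protocol adjusts for confounders elsewhere, but no section fixes an adjusted estimate of concordance against control.

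**How far can the crude contrast move with no treatment effect?** The plan gives no figure for this outcome, so there is none to reproduce. The following is an illustration only.

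Inputs from section 4.5: 55% of patients controlled; two thirds of controlled patients mild to moderate and one third severe to very severe; 285 evaluable patients. Assumed, because the documents give neither: the severe share s of the cohort, and the shares g_m and g_s of mild-to-moderate and severe patients on concordant therapy.

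Control within strata, the same with or without concordant therapy:

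- c_m = 0.55 × (2/3) / (1 − s)
- c_s = 0.55 × (1/3) / s

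Crude control with concordant therapy: p_G = [(1−s)·g_m·c_m + s·g_s·c_s] / [(1−s)·g_m + s·g_s]. For p_N, replace each g by 1 − g. The crude odds ratio is [p_G/(1−p_G)] / [p_N/(1−p_N)].

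Worked case, s = 0.45, g_m = 0.80, g_s = 0.30:

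- c_m = 0.3667/0.55 = 0.667; c_s = 0.1833/0.45 = 0.407.
- p_G = (0.44 × 0.667 + 0.135 × 0.407)/0.575 = 0.606.
- p_N = (0.11 × 0.667 + 0.315 × 0.407)/0.425 = 0.475.
- Crude odds ratio = (0.606/0.394)/(0.475/0.525) = 1.70. Within each stratum it is 1.00 by construction.
- Chance of a significant crude result at N = 285, two-sided 5%: Φ[(|p_G − p_N| − 1.96·SE₀)/SE₁], with SE₀ pooled and SE₁ unpooled. This is Φ[(0.131 − 1.96 × 0.0596)/0.0593] = 0.60.

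| Severe share | Control, mild / severe | Crude OR, g = 30%/80% | Crude OR, g = 80%/30% | Chance of false significance |
|---|---|---|---|---|
| 40% | 61.1% / 45.8% | 0.74 | 1.36 | 24–25% |
| 45% | 66.7% / 40.7% | 0.59 | 1.70 | 59–60% |
| 50% | 73.3% / 36.7% | 0.47 | 2.13 | 88% |

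A milder imbalance (40%/70% or 70%/40%) gives odds ratios from 0.64 to 1.57 and a chance of 11–47%.

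Two cases give no bias. If g_m = g_s, the crude odds ratio is 1.00. If s = 1/3, then c_m = 0.3667/0.6667 = 55% and c_s = 0.1833/0.3333 = 55%, so severity cannot confound.

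The confounder here is severity, which a severity split would remove if it is applied to this comparison. The table therefore shows only the scale that an unsplit confounder of similar strength could reach.

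**The case against.** Several points on the other side stand.

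- **Stratification is not the only method on the page.** A reader might infer that it is, but section 9.3.4 has a multivariable model for control in which medication can be a candidate. It does not cure the problem, because it searches for predictors and does not estimate a named exposure.
- **Time order.** Because medication is also recorded at Visit 0, a reader might infer that patients stepped up after an exacerbation will be counted as guideline-treated and uncontrolled. The documents do not support this. Section 4.4.1.3 ties treatment for this objective to the Visit -1 review, before control is assigned, and a step-up need not make treatment concordant. What remains is that item 5 does not state the time point.
- **No causal claim is made.** A reader might infer that the table will be reported as a treatment effect. The protocol speaks of a role and a distribution, and nowhere says the contrast will be read causally.
- **Concordance is judged relative to phenotype and severity**, and the control thresholds are adapted to severity. It does not follow that concordance is commoner in either stratum, so neither the presence nor the direction of bias is known in advance.
- **Covariate detail can be left to an analysis plan**, which is not shown. That answers the missing list. It does not answer the mismatch that the protocol itself fixes between objective and outcome.

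**Conclusion.** The point holds in limited form. Item 5 of section 4.3.2, followed as written, yields a crude contrast that cannot support objective 2 as worded. The severity split and the stepwise model reduce the gap without closing it.

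No magnitude can be taken from the documents. The range of 0.47 to 2.13 rests on an assumed severe share of 40–50% and assumed concordant-therapy shares of 30–80% by severity. No single odds ratio or direction should be quoted as the expected bias. This concerns one of six secondary outcomes and does not affect the primary comparison.

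**What to change.** In sections 4.3.2 (item 5) and 9.3.4:

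- Classify guideline concordance from the Visit -1 medication review, and state that time point.
- Relate it to control at Visit 0 by logistic regression. Force in concordance and a pre-specified set: BODEx severity, clinical phenotype, exacerbations in the prior 12 months, and country or centre. Do not select these stepwise.
- Keep the distribution table as descriptive, and word objective 2 as an association.

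Adjustment for Visit -1 CAT and mMRC, and a repeat in patients whose medication did not change between Visit -1 and Visit 0, should be at most sensitivity analyses. Patients are already treated at Visit -1, so those scores may reflect the treatment, and the unchanged-medication subset selects on later events. BODEx contains dyspnoea and carries some of the same difficulty, which is a further reason for the associational wording.

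The cost is a wording change, one more model and slightly wider intervals. The clinical covariates are already collected at Visit -1 (section 4.4.1.3 and Table 5), and country follows from the centre.
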